Anticipated adverse events (AE) are events that were not necessarily observed with linzagolix but can be anticipated based on the drug's pharmacological action and/or class effects, such as: increase in liver function test parameters, headache, dizziness, nausea, hyperhidrosis, blood cholesterol increased, low density lipoprotein increased and BMD loss.

In few subjects, an increase in transaminase values exceeding 3>ULN (Upper Limit of Normal) was observed under treatment, most often the increase in transaminase values was reversible and decreased spontaneously under treatment up to normal. These increased transaminase values were not associated with increased bilirubin values.

A borderline effect of linzagolix on the heart rate corrected QT interval was identified with prolongations exceeding the threshold of concern by less than 2 msec. The categorical data for QTc showed no values greater than 480 msec and no changes greater than 30 msec following the suprathreshold and therapeutic doses. Thus, based on the magnitude of the QTc prolongation, the observed effects are not considered to be clinically significant.

The vast majority of related AEs were reported as being of "mild" or "moderate" intensity; only very few related events were reported as being of "severe" intensity.

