Serum calcium: Subjects who have a serum calcium level on treatment above 2.9 mmol/L should have calcium supplements interrupted. If serum calcium level on treatment is above 3.1 mmol/L, calcium supplements and study treatment are to be interrupted. A repeat test of this parameter within 2 weeks under fasting conditions is to be performed. If the results of the repeat remain above 2.9 mmol/L, study treatment should definitively be discontinued and the subject should be advised to consult an endocrinologist for further evaluation.

Bone mineral density loss: subjects who experience more than 8% BMD loss or a Z-score \leq -2.5 at any site (femoral neck, hip or spine) will be discontinued from study treatment and will enter the follow-up period (they will not be eligible to enter the extension study).

Liver function tests: following the Food and Drug Administration (FDA) guidance on drug-induced liver injury, subjects who have an elevation of hepatic enzymes are to be withdrawn immediately from treatment if:

- ALT or AST >8xULN
- ALT or AST >5xULN for more than 2 weeks
- ALT or AST >3xULN and (TBL >2xULN or international normalized ratio INR >1.5)
- ALT or AST >3xULN with the appearance of fatigue, nausea, vomiting, right upper quadrant pain or tenderness, fever, rash, and/or eosinophilia (>5%)

Withdrawn subjects will be followed up until hepatic parameters return to normal.

Sponsor:	ObsEva						
Protocol:	18-OBE2109-00	18-OBE2109-003					
Document Version No.:	V5.0	Document Date:	13-JUN-2022				

ECG : subjects who have a QTcF > 500 ms or increase > 60 ms from the highest value prior to first dose will be withdrawn from study treatment and followed up until return to QTcF < 480 ms or – if not reached after 3 months of treatment cessation- be referred to a cardiologist.

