4.2. General Statistical Methods and Data Handling

4.2.1. General Methods

All output will be incorporated into Microsoft Excel or Word files, sorted and labeled according to the International Conference on Harmonisation (ICH) recommendations, and formatted to the appropriate page size(s).

Tabulations will be produced for appropriate demographic, baseline, efficacy, pharmacokinetic and safety parameters.

For continuous data and for ordered categorical data, if appropriate, the number of non-missing observations, mean, standard deviation, median, first and third quartiles, minimum and maximum will be calculated, including for change from baseline when applicable. The baseline mean will be calculated

Sponsor:	ObsEva		
Protocol:	18-OBE2109-003		
Document Version No.:	V5.0		

for all subjects based on the FAS. For efficacy endpoints and BMD, a baseline mean will also be calculated for each visit using the baseline data for the subset of subjects who attended that visit, such that the same subjects contribute to the mean for the visit and the mean for the corresponding baseline values. Summary statistics will be based primarily on non-missing values. For ordered categorical data and nominal data, absolute counts and relative frequencies (in %) will be calculated.

This study will be conducted at approximately 100 study sites, resulting in only a few subjects per site on average. Subjects from all sites will be pooled and no adjustment for sites will be carried out in the statistical analyses.

Raw and derived data will be listed.

All statistical hypothesis tests and confidence intervals will be two sided.

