4.8.4. Laboratory Data

Clinical laboratory values will be expressed using conventional SI units.

Hematology, coagulation parameters, chemistry and lipids are assessed at screening and at each visit during the treatment period, as well as at M1 FU and M3 FU visits. E2, progesterone (P4) and LH will be assessed at each visit during the treatment period (not at the screening visit), as well as at M1 FU and M3 FU visits. Serum levels of anti-müllerian hormone (AMH) and fasting glucose will be assessed on Day 1 only. Serum levels of sex hormone-binding globulin (SHBG) will be assessed on Day 1 and Month 3 and Month 6 visits. Follicle-Stimulating Hormone (FSH) will be assessed at Month 3 FU at local laboratories for subjects who did not resume menses.

Blood samples will be analyzed by the central laboratory. Due to the COVID-19 situation, some samples may be collected by local laboratories.

Laboratory parameters values will be summarized for each visit for each treatment group and overall including within-group changes from baseline. In the event of repeated values, the last non-missing value per study day/time will be used.

Semi-quantitative laboratory results will be imputed as follows: "<X.X" will be imputed as "X.X/2" and ">X.X" will be imputed as "X.X".

Evaluation of shifts for changes from baseline to all visits, according to the normal ranges with categories "Low", "Normal", "High" where available (for ALT, AST, ALP, Bilirubin, Albumin, Calcium, Creatine Kinase) and according to normal/abnormal/abnormal clinically significant information collected otherwise, will be provided.

For Liver Function Test (LFT) parameters (ALT, AST, ALP, total bilirubin, albumin), evaluation of shifts for changes from baseline to the worst (highest) on-treatment value (including unscheduled assessments) according to the normal ranges with categories "Low", "Normal", "High" will be provided.

Assessments from local laboratories will not be included in summaries and shift tables, as normal ranges may not be comparable.

Sponsor:	ObsEva			
Protocol:	18-OBE2109-0	18-OBE2109-003		
Document Version No.:	V5.0	Document Date:	13-JUN-2022	

All laboratory data will be provided in data listings.

A subset listing will be presented for all abnormal clinically significant laboratory values.

For the lipid panel (Triglycerides, HDL, LDL, Total Cholesterol, LDL/HDL ratio), the percent change from baseline to each on-study visit will also be summarized.

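### Liver enzymes are tabulated as Low/Normal/High shifts and by-visit statistics, with no count by arm at multiples of ULN and no joint ALT/AST–bilirubin (or INR) table

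*SAP*

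**What the plan says.** SAP 4.8.4 gives liver parameters three tabulations.

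- **By-visit summaries.** "Laboratory parameters values will be summarized for each visit for each treatment group and overall including within-group changes from baseline". Under SAP 4.2.1 a continuous summary is more than a mean: "the number of non-missing observations, mean, standard deviation, median, first and third quartiles, minimum and maximum will be calculated".
- **By-visit shift tables** for ALT, AST, ALP, bilirubin and albumin (also calcium and creatine kinase), in three categories set by the normal range.
- **A worst-value shift** for ALT, AST, ALP, total bilirubin and albumin, each taken alone, in the same three categories: "evaluation of shifts for changes from baseline to the worst (highest) on-treatment value (including unscheduled assessments) according to the normal ranges with categories" Low, Normal and High.

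Listings complete the plan: "All laboratory data will be provided in data listings", with a subset listing of abnormal values judged clinically significant. Protocol 13.5.5 likewise plans normal-range shifts and no ULN multiples.

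Two other places use multiples of ULN. Protocol 5.5.3 says that a transaminase rise beyond three times ULN, in a few subjects, "was observed under treatment, most often the increase in transaminase values was reversible"; it adds that bilirubin did not rise with it. Protocol 10.7.2.1 and SAP 2.3 require withdrawal from treatment for ALT or AST above 8 x ULN, above 5 x ULN for more than two weeks, above 3 x ULN with listed symptoms or eosinophilia, and under a combined criterion: "ALT or AST >3xULN and (TBL >2xULN or international normalized ratio INR >1.5".

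**The concern.** The multiples on which earlier rises were described, and on which this trial withdraws women from treatment, appear in no summary by arm. A reader of the study report could not see how many women in each arm exceeded 3, 5 or 8 x ULN. Nor could the reader see how many had a transaminase rise together with raised bilirubin or INR, because each parameter is shifted separately and joint cases cannot be recovered from the margins.

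The SAP grades other safety measures more finely. BMD loss is banded up to a decrease of more than 8%, which is also its discontinuation limit (SAP 4.8.3 and 2.3). LDL and triglycerides have multi-level shift tables, and E2 has three bands (SAP 4.8.4). Liver enzymes also have discontinuation limits but no graded table. Protocol 12.1.5 names no adverse events of special interest, so no liver-specific output arises by that route either.

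**Working it through.** The documents state no figure for the liver analysis, so there is none to reproduce. The check has three parts.

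**1. What the planned categories separate.** Inputs: the normal-range categories in SAP 4.8.4 and the 3, 5 and 8 x ULN multiples in SAP 2.3.

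| ALT, x ULN | SAP 4.8.4 category | Multiples exceeded |
|---|---|---|
| 0.9 | not High | none |
| 1.1 | High | none |
| 2.5 | High | none |
| 3.1 | High | 3 |
| 5.1 | High | 3, 5 |
| 8.1 | High | 3, 5, 8 |
| 9 | High | 3, 5, 8 |

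Six different levels fall in one cell. Cut-offs at 3, 5 and 8 would split that cell into four bands: above 1 to 3, above 3 to 5, above 5 to 8, and above 8.

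**2. Where a marked rise would show.**

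- *By-visit maximum.* It shows one value per arm and visit, in SI units, and does not say how many women crossed a threshold. Under SAP 4.2.9 an unscheduled result enters a visit only if that visit has no assessment of its own, so a peak found on a retest can be missing from these summaries.
- *Worst-value shift.* This table expressly includes unscheduled samples, but it discards magnitude.
- *Adverse event tables.* Protocol 12.1.2 makes a laboratory abnormality reportable when judged clinically significant, for example when it ends treatment. SAP 4.8.2 then counts it by preferred term and under events leading to discontinuation. The ULN level is not shown.
- *What is left.* A rise above 3 x ULN but not above 8, without the listed symptoms or eosinophilia and without bilirubin above 2 x ULN or INR above 1.5, and above 5 x ULN only if for no more than two weeks, meets no stopping rule. Unless the investigator judges it clinically significant, it appears in the arm-level tables only as High or, at most, as a by-visit maximum.

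**3. How likely a case is (illustration only).** Input from SAP 4.1: 150 women per arm. The true rate p of ALT or AST above 3 x ULN is assumed; the documents give no rate. P(at least one case) = 1 − (1 − p)^150.

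| Assumed p | Expected cases, 150p | P(at least one) |
|---|---|---|
| 0.5% | 0.75 | 0.53 |
| 1% | 1.5 | 0.78 |
| 2% | 3.0 | 0.95 |
| 3% | 4.5 | 0.99 |

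A count of zero would also be informative: 0 of 150 gives a one-sided 95% upper limit of 1 − 0.05^(1/150) = 0.020, or 2.0%.

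The arm mean says little about one extreme value. With an assumed ULN of 35 U/L and baseline of 20 U/L, one woman at 9 x ULN moves the mean by (9 × 35 − 20)/150 = 295/150 = 1.97 U/L. Her value of 315 U/L would show as the maximum if it came from a sample included in that visit's summary.

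**The case against.** The strongest reply is that the serious cases are not lost. A woman who meets a liver stopping rule is withdrawn. Withdrawal is itself a ground for reporting an adverse event, and that event is counted by arm in SAP 4.8.2, with reasons for withdrawal in SAP 4.4. A combined ALT and bilirubin case should therefore be recognised as one event. The maximum is printed, every value is listed, and a data monitoring committee reviews unblinded safety data (Protocol 14.5). The SAP follows Protocol 13.5.5 and goes beyond it with the worst-value shift. An individual stopping rule does not by itself oblige the sponsor to produce a matching table.

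Much of this stands. A reader might infer that severe liver cases go uncounted, or can be found only by reading listings; the adverse event route contradicts that. A reader might also infer that combined ALT and bilirubin rises are a known effect of linzagolix. They are not: Protocol 5.5.3 and 5.7 say the earlier rises came without a bilirubin change, and 5.7 describes them as infrequent, transient, moderate and unrelated to dose. Nor do the two documents contradict each other.

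What the reply does not supply is a comparison between arms by level. Adverse event terms carry no ULN multiple and depend partly on investigator judgement, a maximum is not a count, and committee review does not put a table in the study report.

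**Conclusion.** The point holds as a gap in descriptive safety reporting. SAP 4.8.4 pools every value above 1 x ULN, and no arm-level table counts women by multiples of ULN or by a joint transaminase and bilirubin or INR criterion. The gap matters most for isolated rises above 3 x ULN that trigger no withdrawal. For withdrawn cases, what is missing is the level. Because earlier rises came without bilirubin increase, the joint count would show whether that remains so; it would not confirm a known harm.

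Efficacy conclusions, estimands and error rates are unaffected. The absence of the table follows from the text alone. The 78% to 95% chance of at least one case per arm rests on an assumed rate of 1% to 2%; it shows only that a case may well occur, not that one would be missed.

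**What to change.** In SAP 4.8.4 add a descriptive table by arm, based on the maximum on-treatment value including unscheduled samples, giving the number and percent of women with:

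- ALT or AST above 3, above 5 and above 8 x ULN;
- total bilirubin above 2 x ULN;
- ALT or AST above 3 x ULN together with bilirubin above 2 x ULN or INR above 1.5, stating the time window that counts as concurrent.

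Add a plot of peak ALT against peak total bilirubin in multiples of ULN. Two peaks need not coincide, so the plot screens for joint cases and the table row with its window identifies them.

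These are analysis categories built from multiples in SAP 2.3, not a restatement of the stopping rules: there 5 x ULN carries a duration condition, and bilirubin above 2 x ULN is not a criterion alone. No clinical rule changes. The SAP should also say whether local laboratory results, which SAP 4.8.4 leaves out of summaries and shift tables, are left out here too.

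The cost is one table and one figure. ALT, AST, total bilirubin and INR are in the laboratory panel (Protocol Appendix N) and are measured at every treatment visit (Protocol 10.4.8).

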4.8.5. Vital Signs and Physical Examinations

Vital signs include: Height (cm), Weight (kg), Body Mass Index, Systolic Blood Pressure (mmHg), Diastolic Blood Pressure (mmHg) and Heart Rate (beats/min).

Height is assessed at Screening; weight is assessed at Screening, Month 6 and Month 6 of the follow-up period. Other Vital Signs are assessed at Screening, Day 1, every month during the treatment period and at Months 1 and 3 from the follow-up period.

Physical Examination is assessed at Screening, Months 3 and 6 of treatment and follow-up periods.

The actual value and change from baseline to each on study evaluation will be summarized by treatment group and overall for vital signs.

By-subject listings of vital sign measurements will be presented in data listings.

Physical examination results at each time point will be summarized by treatment group and overall; shifts from baseline in physical examination findings to each on study visit will also be presented. All physical examination findings will be presented in a data listing.

Sponsor:	ObsEva			
Protocol:	18-OBE2109-00	18-OBE2109-003		
Document Version No.:	V5.0	Document Date:	13-JUN-2022	

4.8.6. Electrocardiogram

Local 12-lead ECG readings of QTcF are performed at Screening, Day 1 (pre and post-dose) and every month from the treatment period, as well as Months 1,3,6 from the follow-up period.

Baseline will be defined as the highest value prior to first dose.

Actual values and changes from baseline of ECG results will be summarized descriptively, as well as the number and percent of subjects with normal, abnormal and clinically significant abnormal results at baseline and each study visit by treatment group and overall.

All ECG data for each subject will be provided in data listings.

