5.5.1 Pharmacokinetics/Pharmacodynamics

Linzagolix was evaluated in a Phase 1 single/repeated-dose study (Study KLH1101) in which Japanese and Caucasian pre- and post-menopausal women received single doses of linzagolix from 12.5 to 700 mg and repeated once daily doses of 100 to 400 mg once daily for 7 days under fed and fasted conditions. Linzagolix was safe and well-tolerated, showed linear PK, a half-life of about 15–20 hours, and little difference between pre- and post-menopausal women or between Japanese and Caucasian women. There was a dose-dependent suppression of luteinizing hormone (LH), follicle-stimulating hormone (FSH) and E2.

Study 17-OBE2109-001 evaluated the tolerability and PK of a single supra-therapeutic dose of 700 mg linzagolix, and effects of therapeutic and suprathreshold doses of linzagolix on the QTc interval (QT interval corrected for heart rate). Subjects received a 200 mg dose of linzagolix (therapeutic target

exposure), a 700 mg dose of linzagolix (supratherapeutic target exposure), a 400 mg dose of moxifloxacin (positive control), and placebo with an appropriate washout. Linzagolix at 700 mg was well tolerated. A borderline effect of linzagolix on the heart rate corrected QT interval was identified with prolongations exceeding the threshold of concern by less than 2 msec. The categorical data for QTc showed no values greater than 480 msec and no changes greater than 30 msec following administration of the supratherapeutic and therapeutic doses. Thus, based on the magnitude of the QTc prolongation, the observed effects are not considered to be clinically significant.

The open-label study, KLH1103, assessed the absorption, metabolism, and excretion of linzagolix in 6 women of non-childbearing potential. Linzagolix was the predominant component in plasma and all plasma metabolites were present at less than 10% of the total drug related exposure. Similarly, unchanged linzagolix was also a major component in urine and feces. Linzagolix was eliminated in urine (52%) and, to a lesser extent, in feces (38%).

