6.2 SAFETY OBJECTIVES

Safety and tolerability objectives include assessment of BMD, endometrial health, cardiac safety including QT interval prolongation, standard laboratory safety parameters, gynecological assessments and AE frequency including specific hypoestrogenic AEs.

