 - a. Active deep vein thrombosis, pulmonary embolism, or history of these conditions;

- b. Active or recent (e.g. within the past year) arterial thromboembolic disease (e.g. stroke, myocardial infarction);
 - c. Known, suspected, or history of breast cancer;
 - d. Known or suspected estrogen-dependent neoplasia;
 - e. Known protein C, protein S, or antithrombin deficiency, or other known thrombophilia disorders, including Factor V Leiden;
 - f. Migraine with aura;
 - g. History of porphyria;
 - h. Known hypersensitivity to the ingredients.
12. The subject has a history of or current systemic glucocorticoid therapy for treatment of chronic diseases (e.g. Systemic Lupus Erythematosus (SLE), rheumatic arthritis). Inhaled glucocorticoids for e.g. asthma are not considered systemic glucocorticoids.
13. The subject did not respond to prior treatment with GnRH agonists or GnRH antagonists for endometriosis.
14. The subject has alanine aminotransferase (ALT), aspartate aminotransferase (AST), total bilirubin levels or gamma-glutamyl transpeptidase (GGT) level ≥ 2 times the upper limit of normal and indicative of potential liver damage at Screening or Day 1 (subjects with abnormalities at Day 1 will be withdrawn from study at reception of the results).
15. The subject has clinically significant abnormal ECG, or ECG with QTc using Fridericia's correction formula (QTcF) > 450 msec at Screening or Day 1 (prior to dosing).
16. The subject has a known positive human immunodeficiency virus (HIV) or viral Hepatitis serology.
17. The subject has abnormal uterine bleeding of undiagnosed cause.
18. The subject had/has clinically significant findings from a Papanikolaou (PAP) smear test performed within the past 12 months or at the screening visit which will require surgical intervention (e.g. Loop electrosurgical excision procedure (LEEP) or cervical conization).
19. The subject has chronic pelvic pain that, in the opinion of the Investigator, is not caused by endometriosis and requires chronic analgesic or other chronic therapy which would interfere with the assessment of EAP (e.g., interstitial cystitis, presumptive adenomyosis, fibroids, non-endometriosis-related pelvic adhesive disease, post-tubal ligation or irritable bowel syndrome).

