13.5.5 Safety Analysis

The safety and tolerability profile will be assessed versus baseline conditions and differences between treatment groups and descriptive statistics will be produced for both values and change from baseline, where applicable.

Extent of exposure and compliance to treatment will be evaluated.

Concomitant medications will be summarized using the World Health Organization (WHO) Drug Dictionary with frequencies and percentages for each treatment group. All medications administered between the date of the first dose of study drug and the date of the last dose of study drug, inclusive, (i.e., all medications starting or ongoing during the time interval) will be included. Thus, all medications with an end date prior to the first study drug dose will be excluded from the summary table.

An analysis of the TEAEs will be done. AEs will be summarized using the Medical Dictionary for Regulatory Activities tabulated by (MedDRA) dictionary preferred term and system organ class. TEAEs will be summarized with frequencies and percentages for each treatment group. TEAEs are defined as AEs with a start date on or after the first dose of study drug. Adverse events starting more than 30 days following discontinuation of study drug will not be included in summaries of TEAEs but will be summarized separately as post-treatment AEs. Tabulations by severity and drug-relatedness will also be made.

Laboratory parameters values will be summarized for each visit for each treatment group including within-group changes from baseline. Evaluation of shifts for changes from baseline according to the normal range will be provided.

BMD values and corresponding Z-scores will be summarized at baseline and at Month 6 for each treatment group, using the observed data. The within-group percent changes from baseline for BMD values will also be summarized, including 2-sided 95% confidence intervals. Categorical summaries of percent change from baseline will also be produced. The percent changes from baseline to Month 6 will be compared between each of the linzagolix groups and the placebo group via analysis of co-variance with treatment group as the main effect (three values) and including the baseline as a covariate. Sub-group analyses based on demographic and baseline characteristics will be performed for BMD, and will be specified in the SAP. The Safety Analysis Set shall be used when summarizing safety data.

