Appendix A. Schedule of study assessments – Screening and Treatment Periods

Schedule of study assessments – Screening and Treatment Periods								
Timing ¹	Screening Period (up to 3 months ²)	Treatment Period						
		Day 1	M1	M2	M3	M4	M5	M6
Informed Consent	X							
Inclusion-Exclusion criteria	X	X						
Demography, height, weight, medical history	X							X ³
mB&B	X							
Columbia-Suicide Severity Rating Scale	X	X	X	X	X	X	X	X

¹ All post-baseline visits should take place at the end of the defined period (i.e. M1 visit should be scheduled at the end of Month 1, M2 visit should be scheduled at the end of Month 2, etc.). Post-baseline visits dates are calculated from Day 1 visit date. A month is defined as 28 days/4 weeks. Visits should be scheduled \pm 3 days from the calculated date.

² If required for washout of oral contraceptives, other sex hormones, or GnRH antagonists/agonists (provided that the reason for discontinuing the previous GnRH-antagonist is not lack of efficacy), a period of up to 3 months is allowed between signing the informed consent and the screening visit.

³ Only weight will be recorded.

Schedule of study assessments – Screening and Treatment Periods								
Timing ¹	Screening Period (up to 3 months ²)	Treatment Period						
		Day 1	M1	M2	M3	M4	M5	M6
ECG	x	x ⁴	x	x	x	x	x	x
Physical examination	x				x			x
Vital signs	x	x	x	x	x	x	x	x
Urine pregnancy test	x	x	x	x	x	x	x	x
TVUS of uterus	x				x			x
Gynecological examination	x				x			x
Endometrial biopsy	x							x ⁵
Pap smear test	x							
Breast examination (mammogram if required)	x							x

⁴ ECG on Day 1 should be performed twice: once before treatment and once after treatment (just before PK sampling).

⁵ If endometrium thickness in TVUS is ≤ 5 mm, no endometrial biopsy will be necessary.

Schedule of study assessments – Screening and Treatment Periods								
Timing ¹	Screening Period (up to 3 months ²)	Treatment Period						
		Day 1	M1	M2	M3	M4	M5	M6
Clinical laboratory & urinary protein dipstick	x	x ⁶	x ⁶	x	x ⁶	x	x	x ⁶
Blood sample for PK ⁷		x	x	x	x	x	x	x
BMD by DXA	x							x
Adverse events	x	x	x	x	x	x	x	x
Previous/concomitant medication	x	x	x	x	x	x	x	x
Contraceptive dispensing and counselling	x	x	x	x	x	x	x	x
Permitted analgesic prescribing/dispensing	x	x	x	x	x	x	x	x
Vitamin D and calcium dispensing		x	x	x	x	x	x	x
Subject eDiary completion training/check	x	x	x	x	x	x	x	x

⁶ Overnight fasting is required.

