Document Version No.:	V5.0	Document Date:	13-JUN-2022

For other data, unless otherwise specified, baseline will be defined as the data most recently collected prior to the first dose of IMP.

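### SAP 4.8.6 measures ECG change from the highest pre-dose value, so the descriptive mean QTcF change within each arm and overall is shifted downward even with no drug effect

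*SAP*

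**What the plan says.** SAP 4.8.6 schedules QTcF readings at Screening, on Day 1 before and after dosing, monthly during treatment, and at Months 1, 3 and 6 of follow-up. Footnote 4 of Protocol Appendix A confirms the Day 1 pair: "ECG on Day 1 should be performed twice: once before treatment and once after treatment". Two pre-dose readings are therefore planned for every subject.

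The ECG baseline rule is "Baseline will be defined as the highest value prior to first dose", and "Actual values and changes from baseline of ECG results will be summarized descriptively", by treatment group and overall. The general rule in SAP 4.2.10 differs: "For other data, unless otherwise specified, baseline will be defined as the data most recently collected prior to the first dose of IMP". Because that rule yields where something else is specified, 4.8.6 is a declared exception and not a contradiction.

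The highest pre-dose value also appears in the individual QTcF withdrawal criterion (Protocol 10.7.2.1, repeated in SAP 2.3), which uses a rise of more than 60 ms from it. Exclusion criterion 15 removes subjects with QTcF above 450 msec at Screening or at Day 1 before dosing. SAP 4.5.1 lists Fridericia QTc among the tabulated baseline data without saying which baseline definition applies. SAP 4.8.6 plans no between-arm QTcF comparison.

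**The concern.** A single later reading is compared with the larger of two earlier ones. If a subject's QTcF varies at all between readings, the larger one exceeds her average level in expectation, so the average change is below zero without any drug effect. A reference that suits a per-subject rule has been carried into group means.

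The protocol's safety objectives include "cardiac safety including QT interval prolongation", and Protocol 13.5.5 says the "safety and tolerability profile will be assessed versus baseline conditions and differences between treatment groups". The comparison against baseline is the one distorted. A true mean rise would be understated in the within-arm column, and a small one could appear as a fall. In the overall column there is no placebo group to subtract.

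**Working it through.** The documents give no figure for this shift, so there is none to reproduce.

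**Inputs from the documents.** Two pre-dose readings (SAP 4.8.6; Protocol Appendix A, footnote 4); one reading at each monthly visit; about 150 subjects per arm (Protocol 9.1.2); entry cap of 450 msec (exclusion criterion 15).

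**Assumed inputs.** Within-subject SD s = 4 to 12 ms; population mean QTcF 405 to 425 ms; between-subject SD 12 to 18 ms; correlation ρ between the two pre-dose errors of 0 or 0.5; normal errors; no time trend; Screening and Day 1 exchangeable.

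**Step 1: shift without the entry cap.** For two equal-variance normal readings the maximum exceeds the subject's mean by s × √((1 − ρ)/π). This is 0.564 s at ρ = 0 and 0.564 × √0.5 = 0.399 s at ρ = 0.5. The null mean change is minus that amount.

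**Step 2: add the 450 msec cap by simulation.** The cap selects subjects whose pre-dose readings happened to be low, so it pushes the other way. Ranges below cover nine combinations of population mean (405, 415, 425) and between-subject SD (12, 15, 18). Entries are the mean change in ms with no drug effect.

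| s (ms) | ρ | Highest, no cap | Highest, with cap | Last pre-dose, with cap |
|---|---|---|---|---|
| 4 | 0 | −2.3 | −2.3 to −2.1 | 0 to +0.1 |
| 8 | 0 | −4.5 | −4.5 to −3.9 | 0 to +0.4 |
| 12 | 0 | −6.8 | −6.6 to −5.1 | +0.1 to +1.2 |
| 4 | 0.5 | −1.6 | −1.6 to −1.5 | 0 to +0.1 |
| 8 | 0.5 | −3.2 | −3.2 to −2.5 | 0 to +0.6 |
| 12 | 0.5 | −4.8 | −4.6 to −3.0 | +0.1 to +1.6 |

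Using the mean of the two pre-dose readings gives almost the same result as the last reading. The cap reduces the downward shift but does not remove it in any cell.

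**Step 3: compare with sampling error.** With ρ = 0, the variance of the change from the maximum is s²(1 + 1 − 1/π). At s = 8 and n = 150 the standard error of an arm mean is 8 × √(2 − 1/π)/√150 = 0.85 ms, against a shift of about 4 to 4.5 ms.

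**Step 4: check the arm difference.** Simulated trials used 150 per arm, s = 8, ρ = 0, mean 415, between-subject SD 15, the cap, and an illustrative constant 3 ms rise on active treatment:

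| Baseline | Placebo change | Active change | Difference |
|---|---|---|---|
| Highest pre-dose | −4.31 | −1.31 | 3.00 |
| Last pre-dose | +0.14 | +3.14 | 3.00 |

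The within-arm means move; the difference does not. With the highest-value baseline, the illustrative rise of 3 ms is displayed as a fall of 1.3 ms.

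**The case against.** The strongest reply is that little depends on this. The trial is randomised, the placebo column carries the same expected shift, and Protocol 13.5.5 also assesses differences between groups. Actual values are tabulated by visit and all ECG data are listed, so change from another reference can be recomputed. Nothing is tested. All of this stands, and it is why the point is of low severity.

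The second reply is that the choice is deliberate: it uses the protocol's own QTcF reference, and the SAP allows the exception. That also stands. Relative to its stated reference the table reports what it says. It still misleads a reader who takes the mean change as movement from the usual pre-dose level, and the protocol does not require the withdrawal reference for group summaries.

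The third reply is that the size is assumed. This is correct. Screening lasts about three months and Day 1 normally falls early in the menstrual cycle, so exchangeability of the two readings is not established either. The direction needs only some within-subject variability and no offsetting upward trend.

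Two stronger readings are tempting. A reader might infer that the rule hides a drug-placebo difference in QTcF; Step 4 shows that it does not. A reader might also set the shift beside the earlier QT study's "prolongations exceeding the threshold of concern by less than 2 msec" and infer that it could mask the known effect. That figure is an excess over a threshold the documents do not state, not an effect size, so the comparison is not valid.

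**Conclusion.** The concern holds for the descriptive within-arm and overall QTcF change summaries, and only for those. With no drug effect they are expected to show a decrease of about 0.56 within-subject SD for independent pre-dose readings, or 0.40 SD at correlation 0.5. At an assumed SD of 4 to 12 ms that is roughly 1.5 to 7 ms, slightly less with the entry cap. The SD, population mean, between-subject SD and correlation are all assumptions.

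On-study actual values, post-baseline abnormality counts, the individual withdrawal rule and active-minus-placebo differences are untouched. The QTcF row in the SAP 4.5.1 baseline table is ambiguous: if it follows 4.8.6 it is a maximum, and comparing it with on-study actual values would show the same artificial fall. This is a low-severity improvement to a safety display and bears on no efficacy or safety test.

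**What to change.** In SAP 4.8.6, add a change-from-baseline summary that uses either the last pre-dose ECG (the 4.2.10 default) or the mean of the pre-dose ECGs, and state that within-arm and overall QTcF change is interpreted from it. Keep the pre-specified change from the highest value, labelled as matching the individual withdrawal rule, which stays as the protocol states it. Say which definition the QTcF row in SAP 4.5.1 uses. Optionally, show the difference from placebo in QTcF change with a confidence interval.

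The summary should be added, not substituted. SAP V5.0 already contains results from the Month 6 database lock (4.6.1.4), and under SAP 4.3 unblinded results could go to the sponsor once those were incorporated. Section 5 should therefore record the addition as made after that lock.

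The cost is a few SAP sentences, one extra table and a late documented change; no new data are needed. Results are presented after Month 6 and again after follow-up, so the Month 6 ECG output may need a supplement. The new summary keeps a small upward shift from the eligibility cut-off, about 0 to 1.6 ms at SD 4 to 12 ms, which a footnote can state.
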